7.4. Imputation Rules for Missing Dates

The following applies to Part A, Part B, and Part C:

Imputation rules for missing or partial start/stop dates of medication and non-study vaccinations are defined below:

- 1) Missing or partial medication start date:
 - If only Day is missing, use the first day of the month, unless the medication end date is on/after the date of first injection or is missing AND the start month and year of the medication coincide with the start month and year of the first injection. In this case, use the date of first injection.
 - If Day and Month are both missing, use the first day of the year, unless the medication end date is on/after the date of first injection or is missing AND the start year of the medication coincide with the start year of the first injection. In this case, use the date of first injection.
 - If Day, Month, and Year are all missing, the date will not be imputed, but the medication will be treated as though it began prior to the first injection for purposes of determining if status as prior or concomitant.
- 2) Missing or partial medication stop date:
 - If only Day is missing, use the earliest date of (last day of the month, study completion, discontinuation from the study, or death).
 - If Day and Month are both missing, use the earliest date of (last day of the year, study completion, discontinuation from the study, or death).
 - If Day, Month, and Year are all missing, the date will not be imputed, but the medication will be flagged as a continuing medication.

Imputation rules for missing or partial start/stop dates of AEs are defined below:

- 1) Missing or partial AE start date:
 - If only Day is missing, use the first day of the month, unless the AE end date is on/after the date of first injection or is missing AND the start month and year of the AE coincide with the start month and year of the first injection. In this case, use the date and time of first injection, even if AE time was collected.

- If Day and Month are both missing, use the first day of the year, unless the AE end date is on/after the date of first injection or is missing AND the start year of the AE coincides with the start year of the first injection. In this case, use the date and time of first injection, when time is available.
- 2) If Day, Month, and Year are all missing, the date will be imputed as the date of first injection and the AE will be considered as treatment-emergent. However, if the AE end date is prior to the date of first injection, then the AE will be considered a pre-treatment AE. Missing or partial AE end dates will not be imputed.

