- 15. Participant has received a licensed seasonal influenza vaccine within 6 months (180 days) prior to Day 1.
- 16. Participant has participated in any investigational seasonal influenza vaccine study where the study vaccine was administered within 12 months prior to Day 1. Participants who were previously enrolled in mRNA-1010-P303 Part A are not eligible to participate in Part B.
- 17. Participant is not aware whether they have received an influenza vaccine since September 2022.
- 18. Participant has been treated with antiviral therapies for influenza (eg, Tamiflu) within 180 days prior to Day 1.
- 19. Participant has received systemic immunoglobulins or blood products within 90 days prior to Day 1 or plans to receive systemic immunoglobulins or blood products during the study. In addition, participants who have received long-acting biological therapies that affect immune responses (eg, infliximab) within 90 days prior to Day 1, or plan to receive them, are also excluded.
- 20. Participant has donated ≥450 mL of blood products within 28 days prior to Day 1 or plans to donate blood products during the study.

Other Exclusion Criteria

- 21. Participant has participated in an interventional clinical study within 28 days prior to Day 1, based on the medical history interview or plans to do so while participating in this study. Participants may continue in prior interventional study follow-up activities, as long as it does not involve further investigational treatment other than the study intervention described in this protocol (Note: interventions such as counseling, biofeedback, and cognitive therapy are not exclusionary).
- 22. Participant is working or has worked as study personnel or is an immediate family member or household member of study personnel, study site staff, or Sponsor personnel.

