2.5.2.2. Demographics and Baseline Characteristics

Descriptive statistics will be calculated for the following continuous demographic and baseline characteristics:

- Age
- Weight (kg)
- Height (cm)
- BMI (kg/m^2)

The number and percentage of participants will be provided for the following categorical variables:

- Age group 1 (18 to <50 years old, ≥ 50 to <65 years old, or ≥ 65 years old)
- Age group 2 (18 to <50 years old, ≥50 to <65 years old, ≥65 to <75 years old, or ≥75 years old)
- Sex (Male, Female)
- Race (White, Black or African American, Asian, American Indian or Alaska Native, Native Hawaiian or Other Pacific Islander, Other, Unknown, Not reported)
- Ethnicity (Hispanic or Latino, Not Hispanic or Latino, Not Reported, Unknown)
- Previous Year's Flu Vaccine Status (Received/Not received any seasonal flu vaccine anytime in the past 5 to 12 months)

The summaries will be provided separately for all analysis sets (except Solicited Safety Set) defined in Section 2.4.

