2.5.2.4. Prior and Concomitant Medications and Vaccinations

Prior and concomitant medications and non-study vaccinations will be coded using the WHODD, version Mar 2022. Imputation rules for missing dates of medications and non-study vaccinations are detailed in Section 7.4. The summary of concomitant medications will be based on the Safety Set.

Categorization of prior and concomitant medications are summarized in The following applies to Part A, Part B, and Part C:

Table 13 in Section 7.5. The following applies to Part A, Part B, and Part C.

An overall summary of medications and non-study vaccinations including the number and percentage of participants who take the following will be presented by vaccination group:

- Any concomitant medications and non-study vaccinations up to 28 days post-injection
- Non-study seasonal influenza vaccine up to 28 days post-injection
- Systemic steroids (≥ 10 mg/day prednisone or equivalent), immunosuppressants, immune-modifying drugs, immunoglobulins, and/or blood products administered at any time up to 28 days post-injection

The number and percentages of participants with at least one concomitant medication will be summarized by PT and vaccination group. Prior, concomitant medications, and non-study vaccination will be presented in a listing. Medications taken to prevent or treat pain or fever will also be presented in a listing. Concomitant procedures will be presented in a listing.

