3.5. Statistical Analysis

3.5.1. General Considerations

SoA is presented in Section 7.1.2. Additional details are presented in Section 2.5.1.

For the Day 29 primary analysis, the analysis will include all participants' safety data collected up to Day 29 post-vaccination.

Subgroups:

Subgroup Variable*	Categories
Age Group	≥ 18 to <50 years old
	\geq 50 to <65 years old
Previous Flu Season Vaccination	Received
Status	Received from mRNA-1010-P302
	Not Received
Race	White
	Black or African American
	Asian
	American Indian or Alaska Native
	Native Hawaiian or Other Pacific Islander
	Other (combining Not Reported and Unknown)
Sex	Male
	Female
BMI (only for immunogenicity	$<30 \text{ kg/m}^2$
analyses)	$\geq 30 \text{ kg/m}^2$

Table 8 Definition for Subgroups (Part B)

*Subgroup derivations will be based on the information from eCRF.

If the number of participants in a subgroup is less than 10% of sample size in the analysis set, it may be combined with other subgroups for the subgroup analyses.

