7.8. Estimands and Estimand Specifications

The following applies to Part A, Part B, and Part C, unless otherwise specified:

Table 16 Intercurrent Events

Label	Intercurrent Event Type
IcEv1 (early discontinuation or unrelated death)	Early discontinuation from study or unrelated death prior to Day 29, the first post-treatment immunogenicity result available.
IcEv2 (alternative influenza vaccine)	Use of alternative Influenza vaccine prior to Day 29.
IcEv3 (COVID-19 vaccine)	Use of COVID-19 vaccine prior to Day 29.
IcEv4 (prohibited medications)	Use of prohibited medications deemed to impact on immunogenicity prior to Day 29.
IcEv5 (early infection)	Infection starting up to 29 days after IP injection.
IcEv6 (wrong vaccination)	Receiving wrong vaccination.

Abbreviation: IcEv: intercurrent event.

Table 17 Summary of Primary Immunogenicity Estimands with Rationale for Strategies to

Address Intercurrent Events (Part A)

Objective: To evaluate the humoral immunogenicity of mRNA-1010 relative to that of a licensed active comparator (Fluarix Quadrivalent) against 4 vaccine-matched influenza virus A and B strains at Day 29 based on GMT			
Estimand Label	Primary Immune Estimand 1a (on the PP Immunogenicity Set)	Supplementary Immune Estimand 1b	
Estimand Description	Immune response to influenza measured as GMT of vaccine- matched anti-HA level as measured by HAI assay on Day 29 in adults aged at least 18 years inclusive who receive IP administration and complied with immunogenicity blood sampling to have a baseline and Day 29 antibody assessment without significant protocol deviations impacting immune response and no RT-PCR- confirmed influenza between Days 1 to 29.	Immune response to seasonal influenza measured as GMT of vaccine-matched anti-HA level as measured by HAI assay on Day 29 in adults aged at least 18 years or inclusive who receive IP administration irrespective of any significant protocol deviations impacting immune response and complied with immunogenicity blood sampling to have a baseline and Day 29 antibody assessment as measured by HAI assay.	

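### SAP 7.4 dates non-study vaccinations by drug-course rules, so some vaccines given before the study can be counted as concomitant

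*SAP*

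**What the plan says.** SAP 7.4, which covers all three Parts, introduces its first block of rules with "Imputation rules for missing or partial start/stop dates of medication and non-study vaccinations are defined below". No separate rule for vaccinations follows. For a start date with only the year known, the rule is "If Day and Month are both missing, use the first day of the year, unless the medication end date is on/after" the first injection. The exception in full applies "unless the medication end date is on/after the date of first injection or is missing AND the start year of the medication" equals the injection year, and the start is then set to the injection date. A year-only stop date goes to the end of that year, or to study completion, discontinuation or death if earlier. A wholly missing stop date is left blank and the record is flagged as continuing. In SAP 7.5, footnote 1 to Table 13 puts records with a wholly missing end date in the column for end dates on or after injection.

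SAP 2.5.2.4 sends missing vaccination dates to Section 7.4 and uses Table 13 for the prior/concomitant split. Its planned summaries include any concomitant medications and non-study vaccinations up to 28 days, and "Non-study seasonal influenza vaccine up to 28 days post-injection".

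Protocol 2.6.6.2, which Parts B and C adopt by reference, requires any vaccine from the previous 12 months to be recorded. Prior vaccines are therefore in the data to which these rules apply.

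**The concern.** A drug course has a start and an end, and it is cautious to assume that a course of uncertain dates overlaps dosing. A vaccination happens on one day. Carrying the drug rule over has two effects. A year-only start can be moved to the injection day, and a blank end date makes the vaccine look ongoing. Both errors run the same way, from prior towards concomitant.

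What is at stake is the table that shows how many participants in each group received another vaccine, including another influenza vaccine, in the 28 days after dosing. In a trial whose endpoint is an influenza antibody titer, readers use that table to judge whether responses could be confounded by other vaccination. Prior vaccines counted there would mislead them.

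**Working it through.** There is no power or alpha figure to reproduce. The check applies the rules in SAP 7.4 and 7.5 to example records.

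**Dosing year.** The original protocol is dated 28 Feb 2023. The rationale for Amendment 1, dated 10 Oct 2023, reports the Part A primary analysis, which required every participant to have completed Day 29. All Part A doses were therefore in 2023. Amendment 1 added Parts B and C, and no dosing dates are given for them. Dosing in late 2023 is an assumption, so dosing in early 2024 is shown as well.

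**Results.** Table 13's second row is read as starting on or after the injection date. Study completion is taken as injection + 180 days.

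| Start recorded | End recorded | Injection | Start used | End used | Table 13 class |
|---|---|---|---|---|---|
| 2023 | blank | 16 May 2023 | 16 May 2023 | none | concomitant only |
| 2023 | 2023 | 16 May 2023 | 16 May 2023 | 12 Nov 2023 | no column |
| 2023 | 2023 | 11 Dec 2023 | 11 Dec 2023 | 31 Dec 2023 | concomitant only |
| 1 Oct 2022 | blank | 16 May 2023 | 1 Oct 2022 | none | prior and concomitant |
| 2022 | 2022 | 16 May 2023 | 1 Jan 2022 | 31 Dec 2022 | prior |
| 2022 | blank | 16 May 2023 | 1 Jan 2022 | none | prior and concomitant |
| 2023 | 2023 | 15 Jan 2024 | 1 Jan 2023 | 31 Dec 2023 | prior |
| 2023 | blank | 15 Jan 2024 | 1 Jan 2023 | none | prior and concomitant |

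Row 2 has no column because its end date is later than injection + 27 days. Its start is still Day 1, so a count by start date would include it. Table 13's symbols or columns may have been damaged in text extraction, so its apparent gaps are not counted as errors.

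**Is Day 1 a possible date?** Criterion 14 in each Part excludes anyone vaccinated 28 days or less before dosing. Criterion 15 excludes a licensed seasonal influenza vaccine within 150 days (Part A) or 180 days (Parts B and C). A prior vaccine in an eligible participant must lie outside those limits; the rule places it 0 days before dosing.

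**The two routes differ in reach.** The year-only route needs dosing in the recorded year. The blank-end route needs neither a partial start date nor a particular dosing year: in row 4 a fully dated vaccine given 227 days before dosing is still classed as concomitant.

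**Prior-influenza-vaccination windows.** A record of 2022 becomes 1 Jan 2022. That is 423 days before the earliest possible Part A dose (28 Feb 2023), so outside 5 to 12 months, and 243 days before 1 Sep 2022, so outside the Parts B and C window. This matters only if imputed dates feed the status variable, which the SAP does not say.

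**The case against.** The best defence is that little depends on these dates. The affected output is descriptive. The eCRF is not available, so it is unknown whether vaccinations have an end-date field or how programming fills it. Criterion 15 also limits the influenza row for year-only records. For Part A, a 2023 influenza vaccine can be eligible only if dosing is more than 150 days after 1 Jan 2023, that is, after 31 May 2023. These points limit the size of the problem. They do not alter what the rule does when followed as written.

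A reader might infer two larger consequences. The documents do not establish either.

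- **Vaccinated participants become not received.** The Part A window is defined by time ("Received/Not received any seasonal flu vaccine anytime in the past 5 to 12 months"), which makes this tempting. But the SAP says only "Subgroup derivations will be based on the information from eCRF". In Parts B and C one category is vaccination received in mRNA-1010-P302, which no date can yield, so another recorded item must be used. Criterion 17 in Part B excludes anyone to whom "Participant is not aware whether they have received an influenza vaccine since September 2022" applies, and Parts A and C have the same kind of criterion, so the answer is known at entry. A 2023 record moved to Day 1 would stay inside the Parts B and C window, and a vaccine truly given from January to August 2022 lies correctly outside it. SAP Tables 18 and 19 adjust the Parts B and C ANCOVA for status as used for randomization.
- **False intercurrent events remove people from the per-protocol set.** A vaccine dated Day 1 appears to fit "Use of alternative Influenza vaccine prior to Day 29" and the matching COVID-19 vaccine event. But SAP 2.5.2.5 has the sponsor determine excluding deviations before database lock and unblinding, and no text lets an imputed date trigger one. A prior vaccine dated Day 1 would also conflict with the eligibility record and could be queried.

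Both remain risks, because no text rules out use of the imputed dates either.

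**Conclusion.** The point holds as a defect in a stated rule. Followed literally, SAP 7.4 and 7.5 can place prior vaccines among the concomitant ones by two routes: a year-only record matching the dosing year, and a blank end date. The first is certain to operate for Part A records of that kind; for Parts B and C it rests on dosing in 2023. The second depends on whether end dates are left blank, which the documents do not show.

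The number affected is unknown. For scale only, each 1% of randomized participants with such a record would be 24 people in Part A (1% of 2400) and 30 in Part B or Part C (1% of 3000). The demonstrated effect is confined to the SAP 2.5.2.4 vaccination summaries. No change to a coprimary result, subgroup or analysis set is shown. The correction is still worth making: the rule gives a wrong classification where better information, the visit at which the vaccine was reported, should be available.

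**What to change.** In SAP 7.4 and 7.5, take non-study vaccinations out of the medication rules and add:

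1. A vaccination is a single-date event: end date equals start date, and it is never flagged as continuing.
2. A partially dated vaccination is classified as prior or post-dose by the visit at which it was reported. One reported at Screening, or on Day 1 before dosing, is never imputed to the injection date.
3. Imputed vaccination dates do not determine prior-influenza-vaccination status, which comes from the recorded received/not-received answer, and do not trigger the alternative-influenza-vaccine or COVID-19-vaccine intercurrent events (IcEv2 and IcEv3).

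The cost is a few lines of SAP text and the matching programming. The downside is that the exact date of a few prior vaccinations stays unknown in listings.

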7.5. Prior and Concomitant Categorization of a Medication

The following applies to Part A, Part B, and Part C:

Table 13 Categorization of Medication

	Medication End Date		
	< Injection Date of IP \geq Injection Date and \leq Injection Day + 27 Days After		
Medication Start Date		Injection [1]	
< Injection Date of IP [2]	Р	Р, С	
> Injection Date and < 28	-	С	
days after injection			
> 28 days after injection	-	-	

C= Concomitant; P=Prior

[1] Includes medications with completely missing end date.

[2] Includes medications with completely missing start date.

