2.6.6.2. Recording of Concomitant Medications, Concomitant Vaccinations and Concomitant Procedures

The following concomitant medication(s) and vaccine(s) must be recorded in the eCRF:

- Any vaccine (authorized or investigational) administered in the prior 12 months. For authorized influenza vaccines, detailed information regarding which vaccine was administered should be provided if available.
- All prohibited therapies (Section 2.6.6.1) at the time of the Day 1 Visit.
- All concomitant medications taken at the time of the Day 1 Visit through 28 days after study intervention dosing. Antipyretics and analgesics taken prophylactically (ie, taken in the absence of any symptoms in anticipation of an injection reaction) will be recorded as such.
- All non-study vaccines taken through 181 days after study intervention dosing.
- Systemic steroids (≥10 mg/day prednisone or equivalent), immunosuppressants, immunoglobulins and long-acting biological therapies that affect immune responses (eg infliximab), and/or blood products administered at any time during the study period after the study intervention.
- Any concomitant medications relevant to or for the treatment of an SAE, AESI, or MAAE from Day 1 through Day 181 (Month 6)/EoS.
- The participant will be asked in the eDiary if they have taken any antipyretic or analgesic to treat or prevent fever or pain within 7 days after study intervention dosing, including the day of dosing. Reported antipyretic or analgesic medications should be recorded in the source document by the clinic staff during the clinic/in-person visit and safety phone call after study intervention dosing or via other participant interactions (eg, telephone calls).
- All concomitant procedures/surgeries at any time during the study period after study intervention dosing.

Concomitant medications (including vaccinations) will be coded using the WHO Drug Global.

2.6.6.3. Concomitant Medications and Vaccines That May Lead to the Elimination of a Participant From Per-protocol Analyses

The use of the following concomitant medications and/or vaccines will not require withdrawal of the participant from the study but may determine a participant's evaluability in the PP analysis (analysis sets are described in Section 2.9.4):

• Any investigational or nonregistered product (drug or vaccine) other than the study intervention used during the study period.

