- Immunosuppressants administered chronically (ie, more than 14 days in total) during the study period. For corticosteroids, this will mean that prednisone ≥10 mg/day or the equivalent is not permitted. Intra-articular and epidural steroids are not allowed within 28 days before and/or after study intervention dosing. Inhaled, nasal, and topical steroids are allowed.
- Long-acting, immune-modifying drugs administered at any time during the study period (eg, infliximab).
- An authorized or licensed vaccine administered within 28 days of study intervention dosing.
- Immunoglobulins and/or any blood products administered during the study period.

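### SAP Table 13 gives no category to a medication taken within Days 1 to 28 whose known or imputed end date falls after Day 28

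*SAP*

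**What the plan says.** SAP 2.5.2.4 sends the reader to Table 13 for the classification: "Categorization of prior and concomitant medications are summarized in" that table, in SAP 7.5, for all three Parts.

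The table crosses three start-date rows with two end-date columns. The first column holds end dates before injection. The second runs from the injection date to "Injection Day + 27 Days After" injection. A footnote to the second column reads "Includes medications with completely missing end date". The legend has two codes only: "C= Concomitant; P=Prior".

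SAP 7.4 turns some partial stop dates into full ones. If only the day is missing, the rule is to "use the earliest date of (last day of the month, study completion, discontinuation from the study, or death"); if day and month are missing, the last day of the year replaces the last day of the month. A stop date missing altogether is not imputed, and the drug is flagged as continuing.

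Protocol 2.6.6.2 frames collection by when a drug is taken, not when it ends: "All concomitant medications taken at the time of the Day 1 Visit through 28 days after study intervention dosing".

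**The concern.** A drug given in the window but stopped after it falls outside both end-date columns. If the stop date is left blank, the same drug is counted as concomitant. The classification then follows the completeness of date recording rather than exposure, and a better-documented record can drop out of the count.

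Two summaries in SAP 2.5.2.4 are at stake, both on the Safety Set: participants with any concomitant medication up to 28 days post-injection, and participants with at least one concomitant medication by preferred term. A programmer cannot simply fall back on the protocol's wording, because the SAP Introduction says the SAP prevails where methods differ.

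**Working it through.** **Window.** Offsets 0 to 27 days from injection are 28 days, Day 1 to Day 28. This agrees with the 28-day analysis period in SAP 2.5.1.

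**Table 13 applied to example courses.** Dates are offsets in days from injection, with boundaries read generously as inclusive.

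| Start | End | Result |
|---|---|---|
| -10 | +27 | P, C |
| -10 | +28 | no category |
| +5 | +27 | C |
| +5 | +28 | no category |
| +5 | +60 | no category |
| +5 | missing | C |

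One extra day removes the code, and a missing end date restores it.

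**Imputed dates.** Take an injection on 15 November, a stop date recorded only as December, and a participant still in the study at year end. SAP 7.4 gives 31 December, which is 15 + 31 = 46 days after injection, so no category. Offset 27 is 12 December, so the true stop could have been inside the window and the imputation alone moves it out. If the stop month is the month containing Day 28 and only the day is missing, the imputed date falls beyond Day 28 for 353 of the 365 injection dates in 2023, unless study completion, discontinuation or death caps it.

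**Where later end dates can come from.** Ordinary medications are recorded through Day 29 (SAP 7.1 schedules), and the Day 29 visit may be up to 3 days late, at Day 32. After that, only medications linked to an SAE, AESI or MAAE are recorded, to Day 181. Protocol 2.6.6.2 adds systemic steroids, immunosuppressants, immunoglobulins, long-acting biologics and blood products at any time in the study.

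**Share without a category, under stated assumptions.** Assume start days are uniform and a course lasts L days. Of the courses that overlap Days 1 to 28, there are L + 27 possible start days, and L - 1 of these end after Day 28. If every end date is known, the share is (L - 1)/(L + 27). If end dates are known only to Day 32 and later ones are blank, only those ending on Days 29 to 32 are lost: 4/(L + 27) for L of 5 or more.

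| L (days) | All end dates known | Known only to Day 32 |
|---|---|---|
| 7 | 6/34 = 17.6% | 4/34 = 11.8% |
| 14 | 13/41 = 31.7% | 4/41 = 9.8% |
| 30 | 29/57 = 50.9% | 4/57 = 7.0% |
| 90 | 89/117 = 76.1% | 4/117 = 3.4% |

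The share rises with length in one column and falls in the other. If end dates are known to Day 181, those on Days 29 to 181 (153 days) can be lost: 153/207 = 73.9% at 180 days and 153/392 = 39.0% at 365 days. The documents do not say how completely late end dates are recorded, so these figures show a range and do not estimate the effect.

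**The case against.** **The table may be misread.** In the extracted text the two end-date headings run together, so a lost third column cannot be wholly excluded. Two codes, two entries per row and the place of the missing-date footnote all point to two columns. This should be confirmed against the PDF.

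**The intent is clear and the data are kept.** Continuing drugs are concomitant, and drugs started after the window have their own row of dashes, so late exclusion seems meant to depend on the start date. In that row, a known end date by offset 27 is impossible, which also suggests an open-ended column. Every medication still appears in a listing. This supports the fix, but it does not supply the missing category.

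**Stronger readings.** A reader might infer four further things that the documents do not support.

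- *Long courses are missed most.* This tendency holds only among courses with a known end date. Ordinary drugs are recorded only to Day 29, and blank end dates are captured, so the overall direction can reverse.
- *Immune-modifying exposure is under-reported.* SAP 2.5.2.4 gives steroids, immunosuppressants and related products their own line, defined by administration at any time up to 28 days post-injection. A course given on Day 15 qualifies whatever its end date.
- *The per-protocol set is affected.* Protocol 2.6.6.3 does list "Immunosuppressants administered chronically (ie, more than 14 days in total) during the study period" as a possible reason for loss of evaluability. But exclusion runs through significant protocol deviations (SAP 2.5.2.5), prohibited medication is a separate intercurrent event (SAP 7.8), and neither uses Table 13.
- *Drugs started on the injection day have no row.* The strict inequality signs in the row labels may be lost equality bars, so this is a point to confirm and is not counted as an error.

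**Conclusion.** The gap is real on the text as printed, assuming Table 13 has two end-date columns. A medication taken within Days 1 to 28 with a known or imputed end date after Day 28 has no category, while the same medication with a blank end date is concomitant.

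Applied literally, this undercounts two descriptive Safety Set summaries. The number of affected records cannot be derived from the documents, and the shares in the working depend on assumed start days and date recording. No primary or secondary immunogenicity result depends on it. It is a minor point, worth correcting because the outcome should not turn on whether a stop date was filled in.

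**What to change.** Change the second end-date column of Table 13 to: on or after the injection date, or completely missing. Any medication started on or before injection + 27 days and not ended before injection is then concomitant, and also prior if it started before injection. Medications started later keep no code. With this change the share of overlapping courses without a category is 0% for every course length.

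At the same time, confirm that the start-date rows cover the injection day itself, to which SAP 7.4 imputes some partial start dates, and that they leave no gap at the end of the window.

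The cost is one table edit and one line of derivation code, with no new data.
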